15 UNANTICIPATED ADVERSE DEVICE EFFECTS (UADE)

An unanticipated adverse device effect includes any serious adverse effect on health or safety or any life-threatening problem or death caused by, or associated with, a device, if that effect, problem, or death was not previously identified in nature, severity, or degree of incidence. A UADE may also include any other unanticipated serious problem associated with a device that relates to the rights, safety, or welfare of Subjects. Investigators are responsible for reporting any UADEs to Thoratec by telephone, email, or fax, and through the EDC as soon as the study site personnel are made aware of an event, but no later than three (3) calendar days of becoming aware that the event met the criteria for a UADE. Thoratec will review all malfunctions and determine if they are UADEs. Thoratec will report all such effects to the FDA, in accordance with regulatory requirements.

In addition to reporting UADEs to the Study Sponsor, Investigators must report UADEs to their IRB as required.

16 STUDY PROCEDURES AND ASSESSMENTS

Participating centers will utilize their own local laboratories for protocol required laboratory assessments, and will be instructed to follow their institution's requirements for maintenance and/or calibration of laboratory equipment.

16.1 Screening and Enrollment

1. Determine if the Subject is eligible: meets all inclusion and no exclusion criteria. Eligibility criteria can be assessed using data obtained within 90 days of screening, provided the data is representative of the patient's current clinical status.
2. Sign written informed consent. Subjects will be considered enrolled on the day they sign informed consent
3. Only Subjects who have met the eligibility criteria and signed informed consent and who have a scheduled implant date will be randomized through the EDC system. Consent and randomization should occur as close as possible to the implant date; if possible, within 72 hours.
4. Demographics: age, gender, ethnicity, race
5. Intended Use as defined by INTERMACS (Appendix 6)

16.2 Baseline Assessments

The following baseline assessments will be performed within 30 days prior to implant (refer to Section 34, Table 2 for the Study Visit Schedule):

1. Medical History, including cardiovascular history with etiology of HF and duration of HF
2. Physical Exam, including height, weight and vital signs
3. Current Medications (total daily dose): anticoagulation/anti platelet, antibiotics, and cardiovascular medications including ACE inhibitors, ARBs, beta blockers, statins, nitrates, allopurinol, aldosterone blockers, and diuretics including metolazone, hydrochlorothiazide and furosemide
4. Laboratory Assessments:
 - a. Hematology: hemoglobin, hematocrit, percent lymphocytes, platelet count, WBC, PHgb, Bleeding/Coagulation: INR, aPTT/PTT, PT
 - b. Chemistry: Potassium, Blood Urea Nitrogen (BUN), creatinine, uric acid, sodium, eGFR (calculated), serum BNP or NT-proBNP, total protein, albumin or pre-albumin, CRP or hs-CRP
 - c. Lipids: cholesterol
 - d. Liver Enzymes: LDH, AST, ALT, total bilirubin
5. Hemodynamic Measurements
6. Echocardiogram: LVEF, LVEDD, LVESD, AV opening, AI, MR, TR including severity and/or grade.
7. Electrocardiogram (ECG): Heart Rate, QRS duration, Arrhythmias
8. 6 Minute Walk Test (6MWT) (if Subject is able; reason must be provided if not performed)
9. EQ-5D-5L
10. Kansas City Cardiomyopathy Questionnaire (KCCQ)
11. VO2 Max (if Subject is able; reason must be provided if not performed)

12. Functional/clinical status using the following:
 - a. Modified Rankin Score (as determined by an independent assessor; defined as an independent, trained, and certified clinician)
 - b. NYHA Classification (as determined by an independent assessor; defined as an advanced practice practitioner other than the treating investigator)
 - c. INTERMACS Patient Profile (to be assessed immediately prior to implantation; refer to Appendix 2 for definitions)

16.3 Implant

1. Current Medications (total daily dose): anticoagulation/anti platelet, antibiotics, and cardiovascular medications including ACE inhibitors, ARBs, beta blockers, statins, nitrates, allopurinol, aldosterone blockers, and diuretics including metolazone, hydrochlorothiazide and furosemide
2. Implant data/Total CPB time/Blood Product use
3. Pump Parameters (HM II and HM3)
4. HM3 Pump Log files (pump period log, pump event log, controller period log, and controller event log) will be submitted to Thoratec
5. Concurrent Procedures
6. Occurrence of AEs (date of adverse event, determination of seriousness and/or relation to the device, resolution of the adverse event)
7. Device Malfunctions
8. Modified Rankin Score (as determined by an independent assessor; defined as an independent, trained, and certified clinician, and only if a stroke has occurred and 60 days post-stroke)
9. HM II Pump Log files will be submitted to Thoratec (only if a pump-related or possibly related AE or malfunction has occurred)

16.4 Post Op Day 1 (+/- 1 Day)

1. HM3 Pump Log files (pump period log, pump event log, controller period log, and controller event log) will be submitted to Thoratec
2. HM II Pump Log files will be submitted to Thoratec (only if a pump-related or possibly related AE or malfunction has occurred)
3. AP chest x-ray for HM3 subjects; AP feeding tube view x-ray for HM II subjects
4. Echocardiogram or transesophageal echocardiogram (TEE): LVEF, LVEDD, LVESD, AV opening, AI, MR, TR including severity and/or grade (can be performed on post-operative day 0 (post-implant) +2 days)

16.5 1 Week Post-implant (+/- 1 Day)

1. Current Subject Status: whether or not the Subject is ongoing on VAD support
2. Subject Outcome: whether or not the Subject has been transplanted or explanted
3. Current Medications (total daily dose): anticoagulation/anti platelet, antibiotics, and cardiovascular medications including ACE inhibitors, ARBs, beta blockers, statins, nitrates, allopurinol, aldosterone blockers, and diuretics including metolazone hydrochlorothiazide and furosemide
4. Vital Signs
5. Laboratory Assessments:
 - a. Hematology: hemoglobin, hematocrit, percent lymphocytes, platelet count, WBC, PHgb, Bleeding/Coagulation: INR, aPTT/PTT, PT

- b. Chemistry: Potassium, BUN, creatinine, uric acid, sodium, eGFR (calculated), serum BNP or NT-proBNP, total protein, albumin or pre-albumin, CRP or hs-CRP
- c. Lipids: cholesterol
- d. Liver Enzymes: LDH, AST, ALT, total bilirubin
6. Echocardiogram: LVEF, LVEDD, LVESD, AV opening, AI, MR, TR including severity and/or grade.
7. Pump Parameters (HM II and HM3)
8. HM3 Pump Log files (pump period log, pump event log, controller period log, and controller event log) will be submitted to Thoratec.
9. HM II Pump Log files will be submitted to Thoratec (only if a pump-related or possibly related AE or malfunction has occurred)
10. Occurrence of AEs (date of adverse event, determination of seriousness and/or relation to the device, resolution of the event)
11. Device Malfunctions
12. Reoperations/Operative procedures
13. Pump Replacements/Explants/Device Exchanges
14. Driveline Management Assessment
15. Modified Rankin Score (as determined by an independent assessor; defined as an independent, trained, and certified clinician, and only if a stroke has occurred and 60 days post-stroke)

16.6 Discharge (-1 day)

Subjects and his or her family member or caregiver (as applies) must be trained on the operation and care of their LVAS and its components, prior to discharge. Information related to required Subject and caregiver training can be found in the HM II or HM3 Instructions for Use and Patient Handbook. Training documentation will be required to show compliance to the required training.

1. Current Subject Status: whether or not the Subject is ongoing on VAD support
2. Subject Outcome: whether or not the Subject has been transplanted, or explanted
3. Current medications (total daily dose): anticoagulation/anti platelet, antibiotics, and cardiovascular medications including ACE inhibitors, ARBs, beta blockers, statins, nitrates, allopurinol, aldosterone blockers, and diuretics including metolazone, hydrochlorothiazide and furosemide
4. Number of days in ICU
5. Vital Signs
6. Laboratory Assessments:
 - a. Hematology: hemoglobin, hematocrit, percent lymphocytes, platelet count, WBC, PHgb, Bleeding/Coagulation: INR, aPTT/PTT, PT
 - b. Chemistry: Potassium, BUN, creatinine, uric acid, sodium, eGFR (calculated), serum BNP or NT-proBNP, total protein, albumin or pre-albumin, CRP or hs-CRP
 - c. Lipids: cholesterol
 - d. Liver Enzymes: LDH, AST, ALT, total bilirubin
7. Echocardiogram: LVEF, LVEDD, LVESD, AV opening, AI, MR, TR including severity and/or grade.
8. NYHA Classification (determined by an independent assessor defined as an advanced practice practitioner other than the treating investigator)
9. Pump Parameters (HM II and HM3)

10. HM3 Pump Log files (pump period log, pump event log, controller period log, and controller event log) will be submitted to Thoratec
11. HM II Pump Log files will be submitted to Thoratec (only if a pump-related or possibly related AE or malfunction has occurred)
12. Occurrence of AEs (date of adverse event, determination of seriousness and/or relation to the device, resolution of the adverse event)
13. Device Malfunctions
14. Reoperations/Operative procedures
15. Pump Replacements/Explants/Device Exchanges
16. Driveline Management Assessment
17. Collect UB-04 Form
18. Modified Rankin Score (as determined by an independent assessor; defined as an independent, trained, and certified clinician, and only if a stroke has occurred and 60 days post-stroke)

16.7 Subject Follow-up Assessments

16.7.1 Clinic Follow-up Post-implant: 30 Days (+/- 7 days) for 1 month assessment, 90 Days (+/- 30 days) for 3 month assessment, and 180 days (+/- 30 days) for 6 month assessment

The Subject must be seen for a clinic visit to assess the following:

1. Current Subject Status: whether or not the Subject is ongoing on VAD support
2. Subject Outcome: whether or not the Subject has been transplanted, or explanted
3. Current medications (total daily dose): anticoagulation/anti platelet, antibiotics, and cardiovascular medications including ACE inhibitors, ARBs, beta blockers, statins, nitrates, allopurinol, aldosterone blockers, and diuretics including metolazone, hydrochlorothiazide and furosemide
4. Vital Signs
5. Laboratory Assessments:
 - a. Hematology: hemoglobin, hematocrit, percent lymphocytes, platelet count, WBC, PHgb, Bleeding/Coagulation: INR, aPTT/PTT, PT
 - b. Chemistry: Potassium, BUN, creatinine, uric acid, sodium, eGFR (calculated), serum BNP or NT-proBNP, total protein, albumin or pre-albumin, CRP or hs-CRP
 - c. Lipids: cholesterol
 - d. Liver Enzymes: LDH, AST, ALT, total bilirubin
6. Echocardiogram : LVEF, LVEDD, LVESD, AV opening, AI, MR, TR including severity and/or grade.
7. Chest x-ray: PA and Lateral (30 Days and 180 Days only)
8. NYHA Classification (determined by an independent assessor defined as an advanced practice practitioner other than the treating investigator)
9. 6 Minute Walk Test (6MWT) (if Subject is able; reason must be provided if not performed)
10. EQ-5D-5L
11. Kansas City Cardiomyopathy Questionnaire (KCCQ) (90 Days and 180 Days only)
12. Pump Parameters (HM II and HM3)

13. Rehospitalizations
 - a. If rehospitalized, collect UB-04 form
14. HM3 Pump Log files (pump period log, pump event log, controller period log, and controller event log) will be submitted to Thoratec.
15. HM II Pump Log files will be submitted to Thoratec (only if a pump-related or possibly related AE or malfunction has occurred)
16. Occurrence of AEs (date of adverse event, determination of the seriousness and/or relation to the device, resolution of the adverse event)
17. Device Malfunctions
18. Reoperations/Operative procedures
19. Pump Replacements/Explants/Device Exchanges
20. Driveline Management Assessment
21. Modified Rankin Score (as determined by an independent assessor; defined as an independent, trained, and certified clinician, and only if a stroke has occurred and 60 days post-stroke)

16.7.2 Clinic Follow-up Post-implant: 360 Days (+/- 30 days) for 12 month assessment, 540 Days (+/- 30 days) for 18 month assessment, and 720 Days (+/- 30 days) for 24 month assessment

The Subject must be seen for a clinic visit to assess the following:

1. Current Subject Status: whether the Subject is ongoing on VAD support
2. Subject Outcome: whether or not the Subject has been transplanted, or explanted
3. Current medications (total daily dose): anticoagulation/anti platelet, antibiotics, and cardiovascular medications including ACE inhibitors, ARBs, beta blockers, statins, nitrates, allopurinol, aldosterone blockers, and diuretics including metolazone, hydrochlorothiazide and furosemide
4. Vital Signs
5. Laboratory Assessments:
 - a. Hematology: hemoglobin, hematocrit, percent lymphocytes, platelet count, WBC, PHgb, Bleeding/Coagulation: INR, aPTT/PTT, PT
 - b. Chemistry: Potassium, BUN, creatinine, uric acid, sodium, eGFR (calculated), serum BNP or NT-proBNP, total protein, albumin or pre-albumin, CRP or hs-CRP
 - c. Lipids: cholesterol
 - d. Liver Enzymes: LDH, AST, ALT, total bilirubin
6. Echocardiogram: LVEF, LVEDD, LVESD, AV opening, AI, MR, TR including severity and/or grade.
7. Chest x-ray: PA and Lateral (360 Days and 720 Days only)
8. NYHA Classification (determined by an independent assessor defined as an advanced practice practitioner other than the treating investigator)
9. 6 Minute Walk Test (6MWT) (if Subject is able; reason must be provided if not performed)
10. EQ-5D-5L
11. Kansas City Cardiomyopathy Questionnaire (KCCQ)
12. Pump Parameters (HM II and HM3)
13. Rehospitalizations

- a. If rehospitalized, collect UB-04 form
14. HM3 Pump Log files (pump period log, pump event log, controller period log, and controller event log) will be submitted to Thoratec.
15. HM II Pump Log files will be submitted to Thoratec (only if a pump-related or possibly related AE or malfunction has occurred)
16. Occurrence of AEs (date of the adverse event, determination of seriousness and/or relation to device, resolution of the adverse event)
17. Device Malfunctions
18. Reoperations/Operative procedures
19. Pump Replacements/Explants/Device Exchanges
20. Driveline Management Assessment
21. Modified Rankin Score (as determined by an independent assessor; defined as an independent, trained, and certified clinician, and only if a stroke has occurred and 60 days post-stroke)

For a detailed list of assessments and timelines, refer to the Study Visit Schedule in Section 34, Table 2.

16.8 Additional Data Collection:

16.8.1 Pump Log Files

Pump log files will be submitted to Thoratec at defined time points. Pump parameters and pump logs must also be submitted when any pump-related or possibly related AE or malfunction occurs. In addition, Thoratec may periodically collect pump log files, outside of the pre-specified time points and/or may request additional supportive hemodynamic data, if performed as part of the standard of care, for characterization of pump operation and system diagnostic purposes. No specific pre-defined analysis will be performed on this data.

16.8.2 Chest X-Rays

Chest x-rays will be submitted to Thoratec at defined time points. No specific pre-defined analysis will be performed on this data.

16.8.3 Health Economics Data

Upon hospital discharge for the initial implant hospitalization and subsequent re-hospitalizations, UB-04 bills, or similar detailed hospital billing data will be sent to Thoratec.

17 ANTICOAGULATION

Subjects implanted with the HM3 and HM II must be properly anticoagulated to decrease the possibility of thromboembolism and/or pump thrombosis. Anticoagulation guidelines are provided in the HM3 and HM II Instructions for Use (IFU).

18 INFECTION CONTROL GUIDELINES

It is recommended that all investigational centers follow the Patient Care and Management Guidelines developed for the HM II and HM3 LVAS. Guidelines for infection control and driveline management are provided in the HM II and HM3 IFU.

19 BLOOD PRESSURE GUIDELINES

Post-Implantation hypertension may be treated at the discretion of the attending physician. Any therapy that consistently maintains mean arterial blood pressure less than 90 mm Hg should be considered adequate.

20 POST-MORTEM EXAMINATION

All attempts to obtain permission for a full body autopsy should be made for all Subjects that expire during the study. Performance of an autopsy is to be noted on the eCRF and a copy of the autopsy report is to be provided to Thoratec. The primary objective of the autopsy is to determine the cause of death, complications, and other relevant findings. In addition, special attention should be directed toward documentation of Subject-prosthesis interaction and any HM II or HM3 LVAD associated complications.

21 DEVICE RETRIEVAL AND ANALYSIS

Upon Subject death, device explantation, or device malfunction all explanted HM II and HM3 pumps must be retrieved and returned to Thoratec for evaluation and analysis within 48 hours of explant. Devices must be returned in accordance with Thoratec instructions.

Any system component other than the pump, (for example: controller, MPU, batteries) associated with any suspected device malfunction must also be returned to Thoratec for analysis.

22 SUBJECT WITHDRAWAL

The Subject retains the right to withdraw from the study at any time. Should the Subject elect to withdraw from the study, the reason for withdrawal must be documented in the CRF.

Reasons for withdrawal include:

- Subject chooses to withdraw
- Investigator decides to withdraw Subject
- Subject has pump exchanged to any device other than HM II or HM3
- Subject is not implanted with device after randomization.
 - Any subject that is not immediately implanted after randomization, due to deterioration or improvement of their health status, will be followed to implant or outcome or until the cohort is fully enrolled at which time they will be withdrawn as follows:
 - For the short term and long term cohorts, any subject not implanted or who has not achieved an outcome 30 days after the 366th subject is enrolled will be withdrawn.
 - For the powered secondary endpoint, any subject not implanted or who has not achieved an outcome 30 days after the 1028th subject is enrolled will be withdrawn.

- Subject is lost to follow-up
 - Subjects who can no longer be tracked for follow-up data collection at a participating MOMENTUM 3 center will be formally withdrawn from the study.

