13 DATA ANALYSIS AND STATISTICAL ISSUES/JUSTIFICATION FOR STUDY DESIGN

13.1 General Statistical Analysis Plan:

The HM3 IDE study will investigate the safety and effectiveness of the HM3 LVAS for short term hemodynamic support, such as a bridge to cardiac transplantation (BTT) or myocardial recovery, or as long term support, such as destination therapy (DT). The HM3 IDE study is a prospective, multicenter, unblinded, randomized, controlled, non-inferiority study comparing the HM3 LVAS to the HM II LVAS.

In general, continuous data will be presented as the number of Subjects, mean with standard deviation, median, and minimum and maximum values. Categorical data will be reported as frequencies and percentages. Adverse events will also be reported as rates per patient year. Only adverse events that occur after the start of the implant procedure will be analyzed. Survival data will be presented using the Kaplan-Meier product limit method.

Data will be analyzed using the intent-to-treat method (ITT) defined as all randomized Subjects. Every effort will be made to avoid cross-over but in the event they occur, data will also be analyzed “as randomized” for efficacy analysis and “as treated” for safety analysis and all other secondary endpoints.

Every effort will be made to collect all required data. Missing primary endpoints will be imputed using multiple imputation techniques. Missing secondary endpoints will not be imputed, except as described below. A one-sided 0.025 level of significance or two-sided 0.05 level of significance will be used to declare statistical significance as outlined below. Multiplicity adjustments will not be made unless specified below.

Statistical analysis will be performed using SAS version 9.1 or higher.

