13.3 Study Hypothesis

13.3.1 Short Term Support:

The short term study endpoint is a composite of survival to transplant, myocardial recovery or 6 months of support (whichever occurs first) free of a debilitating stroke (modified Rankin Score > 3) or reoperation to replace the original pump. A Subject will be considered a success if they are:

- Electively transplanted or explanted for myocardial recovery prior to 6 months or
- Alive at 6 months, and
 - Have not experienced a stroke with a modified Rankin Score > 3, and
 - Have not received a device replacement or exchange, and
 - Have not received an urgent transplant due to a LVAS malfunction.

A Subject will be considered a failure if they:

- Expire prior to 6 months, or
- Experience a stroke with a modified Rankin Score > 3 prior to 6 months, or
- Have a device replaced or exchanged or deactivated for reasons other than myocardial recovery prior to 6 months, or
- Have received an urgent transplant due to a LVAS malfunction prior to 6 months, or
- Have withdrawn from the study for any reason prior to 6 months

HM3 short term success rate will be compared to that of the HM II control in a non-inferiority manner. The null and alternative hypotheses are:

$$H_0: \pi_{HM3} \leq \pi_{HM II} - \Delta$$

$$H_A: \pi_{HM3} > \pi_{HM II} - \Delta$$

where π_{HM3} and $\pi_{HM II}$ are the short term success rates of HM3 and HM II, respectively, and where Δ is the non-inferiority margin.

13.3.2 Long Term Support:

The long term study endpoint is a composite of survival to transplant, myocardial recovery or 24 months of support (whichever occurs first) free of a debilitating stroke (modified Rankin Score > 3) or reoperation to replace the original pump. A Subject will be considered a success if they are:

- Electively transplanted or explanted for myocardial recovery prior to 24 months or
- Alive at 24 months, and
 - Have not experienced a stroke with a modified Rankin Score > 3, and
 - Have not received a device replacement or exchange, and
 - Have not received an urgent transplant due to a device malfunction.

A Subject will be considered a failure if they:

- Expire prior to 24 months, or
- Experience a stroke with a modified Rankin Score > 3 prior to 24 months, or
- Have a device replaced or exchanged or deactivated for any reason other than myocardial recovery prior to 24 months, or
- Have received an urgent transplant due to a LVAS malfunction prior to 24 months, or

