- Have withdrawn from the study for any reason prior to 24 months

The 24 month success rate of the HM3 Subjects will be compared to the HM II control. The null and alternative hypotheses are:

$$H_0: \pi_{HM3} \leq \pi_{HM II} - \Delta$$

$$H_A: \pi_{HM3} > \pi_{HM II} - \Delta$$

where π_{HM3} and $\pi_{HM II}$ are the long term success rates of HM3 and HM II, respectively, and where Δ is the non-inferiority margin.

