13.16.2 KCCQ

The KCCQ score will be assessed at baseline and then at 3, 6, 12, 18, and 24 months. Data will be analyzed using mixed modeling by comparing the KCCQ score at each assessment interval to the baseline score. The Short Term indication will be limited to the 3 and 6 month assessments. The Long Term indication will include all assessments until 24 months or outcome, whichever occurs first.

13.17 Powered secondary analysis:

In addition to the primary outcome, the study will be powered to test if HM3 pump reliability is superior to HM II by analyzing the incidence of pump replacements. Randomization described in Section 13.4 will continue beyond the Subjects needed to power the primary endpoint until a sufficient sample size has been enrolled to test the secondary endpoint. The null and alternative hypotheses are:

$$H_0: \pi_{HM3} \geq \pi_{HM II}$$

$$H_A: \pi_{HM3} < \pi_{HM II}$$

where π_{HM3} is the HM3 pump replacement rate and $\pi_{HM II}$ is the HM II pump replacement rate.

Based on data contained in Thoratec's device tracking database, 7% of the HM II Subjects receive a pump replacement by 24 months. If we assume that HM3 pump replacements will be reduced to 3% at 24 months, then 1028 Subjects will be needed to prove superiority with a power of 80% and alpha = 0.05 (2-sided).

Once the 366 Subjects needed for the long term indication are enrolled, Thoratec will continue to randomize 662 more Subjects for this secondary analysis. Data for this secondary analysis is not needed for the short or long term indications, but rather will be used to provide additional labeling information.

The Subjects will be followed for 24 months or to outcome, whichever occurs first, and analyzed using the Fisher's exact test. Treatments will also be compared on time-to-pump replacement using the log-rank test where Subjects without a replacement are censored at last known follow-up. Otherwise, there will be no imputation of missing data for this analysis.

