23 RISKS

The HM3 LVAS is an investigational device and has not been approved by the U.S. FDA or any other regulatory authority. Extensive testing has been performed on the device in the laboratory and in animal studies providing assurance to proceed with human use of the HM3 LVAS.

The potential risks including anticipated adverse events and possible interactions with concomitant medical treatments related to use of the HM3 are expected to be similar to those seen with commercially available mechanical circulatory support.

The recent HM II BTT Post-approval study followed 169 patients from 53 sites in the United States for 6 months. The HM II DT Post-approval study followed 247 patients from 61 hospitals in the United States for 24 months. If it is assumed that adverse event rates experienced in the HM3 study will be within the upper 99% confidence interval of that reported in the HM II Post-approval studies, then the expected rates for HM3 adverse events³ would be as reported in Table 1. In addition, the recent commercial data, as reported by Kirklin et al, shows that freedom from pump exchange or death due to pump thrombosis at 6 months is 94%¹¹.

Table 1 – Expected Incidence Rate of Adverse Events

Adverse Event	Incidence Rate at 6 Months³ Less than or Equal to:	Incidence Rate at 24 Months¹² Less than or Equal to:
Death	11%	47%
Bleeding	56%	62%
Cardiac Arrhythmia	37%	45%
Hemolysis	7%	11%
Hepatic Dysfunction	12%	12%
Driveline Infection	26%	22%
Blood Infection	28%	26%
Other Localized Infection	39%	53%
Stroke	12%	19%
Other Neurological Dysfunction	9%	18%
Pericardial Drainage	17%	13%
Psychiatric Episode	15%	19%
Renal Dysfunction	17%	25%
Respiratory Failure	29%	34%
Right Heart Failure	23%	25%

Adverse Event	Incidence Rate at 6 Months³ Less than or Equal to:	Incidence Rate at 24 Months¹² Less than or Equal to:
Venous Thromboembolism	12%	9%
Device Thrombosis	3% ¹³	7%
All Other Adverse Events	5%	3%

³Starling RC, Naka Y, Boyle AJ et al. Results of the Post U.S. Food and Drug Administration-Approval Study with a Continuous Flow Left Ventricular Assist Device as a Bridge to Heart Transplantation, J Am Coll Cardiol 2011; 57:1890-1898

¹² Thoratec Final Post Approval Report to the FDA on the HM II Destination Therapy – INTERMACS Post Approval Study

¹³ Thoratec Data : HM II Bridge to transplant – INTERMACS Post Approval Study

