29.2 Device Accountability Records

The Thoratec HeartMate 3 LVAS is an investigational device. All investigational devices must be stored in a location that is accessible only by authorized study personnel. The Sponsor and investigator must maintain accurate Device Accountability records indicating the date of shipment, receipt of product, date of use and assignment to study Subject, and final disposition (return) of the devices.

Traceability of investigational devices will be maintained by the Sponsor through the use of unique serial and/or lot numbers.

All unused investigational components must be returned to the Sponsor, as directed.

NOTE: Investigational devices should only be used on Subjects who are enrolled in the study and randomized to the HM3 arm.

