29.3 Source Documentation

Original documentation supporting the data recorded on the eCRFs must be maintained, and include clinical charts, medical records, laboratory reports, physician referral or consultation letters, X-ray reports, etc. Adverse events which are managed at a health care facility other than the study site must be reported on an eCRF and every attempt must be made to obtain source documentation from that facility.

During monitoring visits, source documents will be reviewed to ensure accuracy and validity of data recorded on the eCRFs. Source document verification will be performed by Thoratec, or its designee, with due regard to Subject confidentiality.

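### A subject who moves to a non-participating center is withdrawn and can be scored a primary-endpoint failure, although the true outcome could often still be obtained

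*Protocol*

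**What the plan says.** Protocol Section 22 lists loss to follow-up among the reasons for withdrawal and explains it in a single sentence: "Subjects who can no longer be tracked for follow-up data collection at a participating MOMENTUM 3 center will be formally withdrawn from the study". The sentence applies to both arms. Transfer to another participating center does not trigger it. Section 22 sets out no telephone contact, vital-status check or record request after such a withdrawal.

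The primary endpoint definitions (Protocol 13.3, repeated in SAP 8.2) then list among the failures "Have withdrawn from the study for any reason prior to 6 months" and, for the long-term endpoint, "Have withdrawn from the study for any reason prior to 24 months". Protocol 13.1, repeated in SAP Section 7, gives a different treatment: "Missing primary endpoints will be imputed using multiple imputation techniques".

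Elsewhere, survivors are censored at last known follow-up (Protocol 13.9). For the powered pump-replacement test, after the log-rank censoring rule, Protocol 13.17 says: "Otherwise, there will be no imputation of missing data for this analysis".

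The protocol already expects sites to pursue outside information. Section 29.3 says "Adverse events which are managed at a health care facility other than the study site must be reported on an eCRF" and asks for every attempt at the outside source documents.

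On device status, Protocol Section 1 describes HM II as FDA-approved. Section 23 says HM3 "has not been approved by the U.S. FDA or any other regulatory authority", and Section 29.2 says "Investigational devices should only be used on Subjects who are enrolled in the study and randomized to the HM3 arm".

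**The concern.** Someone who is alive, willing and free of stroke and pump exchange, but now cared for outside the network, meets the Section 22 test. Under 13.3 that change of address counts the same as death, disabling stroke or pump replacement. The same subject is censored for survival, and a later pump replacement may go unseen. Yet vital status, transplant or explant, stroke and pump replacement are hard facts that can usually be learned from a distance. The plan therefore creates misclassification and missing data that it could avoid.

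Two features raise the stakes. First, the trial is an unblinded non-inferiority comparison, so a spurious excess of HM II failures would make HM3 look better than it is. Second, a difference in loss between arms is plausible: a marketed pump may be easier to manage at a non-study center than an investigational one. The sample size has no margin for this. Its only inflation, 9 subjects per arm, is for early transplant or recovery (Protocol 13.5).

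**Working it through.** **Step 1. Reproduce the plan's sample sizes.** Inputs: success rates 85% v 87% (6 months) and 50% v 55% (24 months), margin 10 points, one-sided alpha 0.025, power 80%, Farrington-Manning (Protocol 13.5; SAP 8.4).

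n per arm = [(1.96·s0 + 0.8416·s1) / (difference + 0.10)]², where s0 uses the success rates fitted under the null and s1 the assumed rates.

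- 6 months: s0 = 0.5082, s1 = 0.4905, so n = [(0.9961 + 0.4128)/0.12]² = 137.9, i.e. 138. The SAP states 138.
- 24 months: s0 = 0.7027, s1 = 0.7053, so n = [(1.3773 + 0.5936)/0.15]² = 172.6, i.e. 173. The SAP states 174, which the unpooled formula gives exactly.

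With the 9 added per arm, the planned numbers are 147 and 183.

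**Step 2. Effect of failure scoring.** The documents give no withdrawal or relocation rate, so w is an assumption. If a share w of an arm is withdrawn for moving before any failure event, independently of outcome, and scored as failure, observed success is p(1 − w). With losses in HM II only, the difference shifts toward HM3 by p·w: 0.85 points per 1% at 6 months and 0.50 points per 1% at 24 months.

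Type I error is taken with HM3 truly at the margin (75% v 85%; 40% v 50%). Example, w = 2%, about 3 of 147 HM II subjects:

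- 6 months: observed HM II success 0.833, difference −0.083. z = (0.017·√147 − 1.96·0.5717)/0.5715 = −1.60, giving 5.5%.
- 24 months: observed HM II success 0.49, difference −0.09. z = (0.010·√183 − 1.96·0.6993)/0.6999 = −1.76, giving 3.9%.

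The table compares this with exact binomial enumeration of the rule that the lower 95% Wald limit exceeds −10%. The last two columns assume that movers do better than their arm (90% success at 6 months, 60% at 24 months), so that failure scoring costs HM II more.

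| HM II excess | 6 mo, FM | 24 mo, FM | 6 mo, exact | 24 mo, exact | 6 mo, exact, movers 90% | 24 mo, exact, movers 60% |
|---|---|---|---|---|---|---|
| 0 | 2.5% | 2.5% | 2.6% | 2.4% | 2.6% | 2.4% |
| 1% | 3.8% | 3.1% | 3.9% | 3.0% | 4.0% | 3.1% |
| 2% | 5.5% | 3.9% | 5.7% | 3.7% | 5.9% | 4.0% |
| 3% | 7.7% | 4.8% | 7.9% | 4.5% | 8.4% | 5.1% |
| 5% | 14.0% | 7.1% | 14.2% | 6.7% | 15.4% | 8.1% |

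**Step 3. Losses in both arms** (exact, movers succeed at the arm rate):

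| HM II / HM3 withdrawn | 6 months | 24 months |
|---|---|---|
| 5% / 5% | 3.2% | 3.0% |
| 3% / 2% | 4.2% | 3.2% |
| 2% / 5% | 0.9% | 1.5% |

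The problem is the imbalance. Equal loss does little to type I error, and the reverse imbalance makes the test conservative against HM3.

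**Step 4. Pump replacement.** Inputs: 7% v 3%, 514 per arm, two-sided 0.05 (SAP 8.16). The continuity-corrected formula gives 514, as stated; exact Fisher power is 81.6%. Suppose a share x of HM II subjects moves, half of their replacements go unseen, and unseen counts as none. The observed HM II rate is then 7%·(1 − x/2):

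- x = 3%: 6.895%, power 79.7%
- x = 5%: 6.825%, power 78.4%
- x = 10%: 6.65%, power 75.0%

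**The case against.** A reader might infer that the rule falls mainly on HM II and so pushes the primary comparison toward HM3. The documents do not support that. Section 22 treats the arms alike. Section 29.2 concerns in whom an investigational device may be used, and Section 31.4 concerns training of study staff; neither says where an implanted subject may later receive care. No withdrawal rates by arm are given. HM3's status might also change during follow-up, since the PMA is to be submitted on 6-month data. The asymmetry is a plausible inference from approval status and no more.

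Nor does the text say that data collection must stop. The Section 22 sentence is about subjects who cannot be tracked, and an enrolling center that still obtains records might claim to be tracking the subject. Where the protocol means that follow-up ends, it says so: Protocol Section 5 does for exchange to another device. For a move, the end of collection is implied by the lack of any route to continue it.

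The direction of bias also depends on failure scoring. Under the imputation rule of Protocol 13.1, a shift toward HM3 is not shown, and if data are missing at random, imputation would not by itself favor HM3. For pump replacement, unseen HM II events work against HM3, and Protocol 13.17 does not say that a missing subject counts as not replaced.

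There are partial safeguards. Explanted pumps from both arms must be returned (Protocol Section 21), reasons for withdrawal are recorded (Section 22), and the SAP adds a Per Protocol efficacy analysis that excludes subjects missing more than two visits after initial discharge (8.1.4).

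All of this stands and limits the claim about bias. It does not remove the defect: a subject whose outcome could be learned may still be scored a failure, and the plan does not settle whether failure scoring or imputation governs.

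**Conclusion.** The point holds as avoidable misclassification and missing data, with a possible but unproven bias between arms. The documents establish the withdrawal trigger, the failure rule and the unreconciled imputation rule. They do not establish that more HM II than HM3 subjects would be withdrawn.

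If failure scoring applies and HM II withdrawals exceed HM3 withdrawals by 1 to 5 percentage points, one-sided type I error rises from about 2.5% to about 4–15% at 6 months and 3–8% at 24 months. The range covers both assumptions about movers' success. Every withdrawal rate here is assumed. The secondary power loss, up to about 6.6 points at 10% moved (81.6 − 75.0), needs the further assumptions that half of movers' replacements go unseen and that unseen counts as none.

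The change is worth making whichever scoring rule is meant and whichever arm would lose more subjects.

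**What to change.** 1. Amend the loss-to-follow-up bullet in Section 22 so that a consenting subject who moves care stays in the study. At each scheduled time point to 24 months, in both arms, the enrolling center obtains vital status, transplant or explant, stroke with modified Rankin score, and pump replacement, by telephone and outside records as Section 29.3 already envisages.
2. Reserve lost to follow-up for subjects whose status cannot be found by these routes.
3. State in Protocol 13.1 and 13.3, and in SAP Sections 7 and 8.2, whether failure scoring or multiple imputation applies to those subjects. Use the other rule, or a tipping-point analysis by arm, as a sensitivity analysis.
4. State in Protocol 13.17 and SAP 8.16 how a subject with incomplete follow-up enters the Fisher test.
5. Report withdrawals by arm and reason.

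The sponsor's device tracking database, the source of the 7% HM II figure, might serve as a cross-check on pump replacement. The documents do not say whether it covers HM3, so that should be confirmed first.

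The cost is protocol and SAP wording plus a few calls or record requests by existing coordinators. Walk test, NYHA class and laboratory values will still be missing for moved subjects, and a Rankin score taken remotely is less exact.
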